2.4.3.6. Statistical Analysis

The statistical analysis, including sample size justification and power considerations are given in Section 12.

3. PARTICIPANT SELECTION AND ENROLLMENT PROCEDURES

3.1 Inclusion Criteria

- a. Biopsy confirmed diagnosis of squamous cell carcinoma of the head and neck
- b. Subjects with recurrent disease or a new primary will be allowed
- c. Planned standard of care surgery with curative intent for squamous cell carcinoma
- d. *** SNB only cohort:** Subjects diagnosed with a T1-T2 stage tumor, any subsite within the head and neck that is amenable to local sentinel node tracer injection and are scheduled to undergo surgical resection of the tumor, including a sentinel node biopsy
- e. *** Neck dissection only cohort:** Subjects diagnosed with any T stage, any subsite within the head and neck that are scheduled to undergo surgical resection, including a (modified) neck dissection
- f. Age \geq 19 years
- g. Karnofsky performance status of at least 70% or ECOG/Zubrod level 1
- h. Have acceptable hematologic status, coagulation status, kidney function, and liver function including the following clinical results:
 - i. Hemoglobin \geq 9 gm/dL
 - ii. White blood cell count $>$ 3000/mm³
 - iii. Platelet count \geq 100,000/mm³
 - iv. Serum creatinine \leq 1.5 times upper reference range

**Only one criterion to be checked for each participant – either “d” or “e”.*

3.2 Exclusion Criteria

- a. -Myocardial infarction (MI); cerebrovascular accident (CVA); uncontrolled congestive heart failure (CHF); significant liver disease; or unstable angina within 6 months prior to enrollment
- b. History of infusion reactions to monoclonal antibody therapies
- c. Pregnant or breastfeeding
- d. Magnesium or potassium lower than the normal institutional values
- e. Subjects receiving Class IA (quinidine, procainamide) or Class III (dofetilide, amiodarone, sotalol) antiarrhythmic agents
- f. Subjects with a history or evidence of interstitial pneumonitis or pulmonary fibrosis

g. Hypersensitivity to dextran and/or modified form thereof

3.3 Informed Consent Process

All participants must be provided a consent form describing the study with sufficient information for participants to make an informed decision regarding their participation. Participants must sign the IRB-approved informed consent prior to participation in any study specific procedure. The participant must receive a copy of the signed and dated consent document. The original signed copy of the consent document must be retained in the medical record or research file.

3.4 Enrollment Process

After signing an informed consent, subjects will be assigned a unique subject identification number based on the OnCore number and sequential numeric code (ie, SLN0028-001, -002, etc). The subject identification number will be used on all subject specific Case Report Forms (CRFs) and serious adverse event (SAE) forms. Participant information should be entered into OnCore within 5 business days.

3.5 Study Timeline

Primary Completion:

The study will reach primary completion 18 months from the time the study opens to accrual; we anticipate enrolling 1 to 2 subjects per month from the start of the study.

Study Completion:

The study will reach study completion 24 months from the time the study opens to accrual.

The anticipated study start date: December 2018 – January 2019

The anticipated study completion date: December 2020

4. TREATMENT PLAN

4.1 Treatment Schedule

Subjects will receive intravenous panitumumab-IRDye800 (50 mg) 1 to 5 days prior to surgery. Then on the day before surgery, subjects in Cohort 1 will receive a local injection with 2 mCi Lymphoseek followed by lymphoscintigraphy and SPECT/CT imaging to determine the number and location of LNs. In the operation theatre, using a combination of fluorescence imaging and radio-tracing, the LNs of the neck will be evaluated and scored (Section 2.4, Figure 1).

4.2 Administration of panitumumab-IRDye800

Administration of panitumumab-IRDye800 will be performed consistent with institutional policy for administration of panitumumab. The solution will be diluted to a total volume of 100mL using 0.9% sodium chloride injection, USP. Dosage level will be 50 mg panitumumab-IRDye800 (< 1/12 of a therapeutic dose of panitumumab). Administration of panitumumab-IRDye800 will occur by IV over 15 (\pm 5) minutes. Subjects will be observed for 30 (\pm 10) minutes after administration. Additional treatment for infusion reactions and electrolyte imbalances may be given following institutional policy.

Premedication will be delivered prior to the infusion for each subject at the discretion of the treating physician according to routine institutional protocols for delivery of panitumumab.

Treatment will be given in an infusion facility that routinely administers experimental chemotherapeutic infusions and is equipped with emergency equipment and medication along with medical personnel in the event that the subject experiences a severe reaction.

The infusion(s) will be stopped if deemed necessary with the onset of any significant signs of reaction. Steroids and other supportive medications may be administered and infusion resumed at the discretion of the treating physician. If a subject experiences a serious reaction that prevents completing the study infusion(s), the subject will be observed; but will not complete their study infusion(s). Any subject who does not receive the full panitumumab-IRDye800 dose will be considered withdrawn from the study and not count towards cohort accrual.

With a single dose at the levels proposed the half-life is expected to be approximately 2.3 days or less. Clearance of panitumumab occurs through the binding in the liver and through the reticuloendothelial system as occurs with endogenous immunoglobulin.

4.3 Administration of Lymphoseek (^{99m}Tc-Tilmanocept)

Lymphoseek is supplied as a unit dose from Cardinal Health.

The radiopharmaceutical Lymphoseek will be administered locally at the Division of Nuclear Medicine. A total of 4 peri-tumoral injections of 0.1 mL of Lymphoseek will be given with a total dose of 2 mCi Lymphoseek injected. Per physicians discretion, local anesthesia may be used (ie, viscous lidocaine, lidocaine spray).

Radiation risk Lymphoseek: Exposure to radiation causes both direct DNA damage (single-strand or double-strand DNA breaks) via ionization (energy is transferred to electrons and the atom loses an electron becoming ionized) and indirect damage via the formation of free radicals. Adhere to As Low as Reasonably Achievable (ALARA) principles (dose recommendations) and ensure safe handling (time, distance, and shielding) to minimize the risk for excessive radiation exposure to either patients or health care workers.

Technetium-99m decays by isomeric transition with a physical half-life of approximately 6 hours. The estimated local radiation dose varies greatly on the time to surgery and the administered dose as well as the injected location (27). The recommended dose of Lymphoseek is 0.5 mCi (18.5 MBq) as a radioactivity dose and 50 mcg as a mass dose for a 1-day protocol (i.e., surgery is performed within 15 hours) and 2 mCi (74 MBq) for a 2-day protocol (i.e., surgery is performed the day after injection of Lymphoseek).

No specific **adsorbed radiation dose for Lymphoseek** has been reported **in patients** with oral cavity carcinoma, however, for breast cancer and melanoma adsorbed radiation doses are reported in the package insert of Lymphoseek when a dose of 0.5 mCi is injected (Table 2). The effective dose equivalent for males and females are 0.20 and 0.25 mSv in melanoma and 0.30 and 0.33 mSv in breast cancer, respectively. These doses are in line with previous SNB reports from amongst others Memorial Sloan Kettering Cancer Center (80). As for the absorbed radiation dose for the surgical staff in the operation room, this is < 0.0001 mSv per operation with a maximum dose of < 0.0002 mSv to the surgeon (27) – these doses are further minimized when the surgery is performed > 24 hours after radiotracer administration. Monitoring of the operation room personnel and additional shielding is therefore not required.

For a 2 mCi administrated Lymphoseek dose, using Table 2 as reference, we estimated the effective dose equivalent for males and females being 0.810 and 1.05 mSv in melanoma and 1.18 and 1.32 mSv in breast cancer, respectively. **Extrapolating this to our HNSCC subjects, the total amount of radiation from one SNB procedure using Lymphoseek will then range 1.41 to 1.78 mSv in males and 1.65 to 1.97 mSv in females – this includes a 0.6 mSv dose that the subject will receive when the low-dose CT is acquired. This is approximately 4% of the total radiation a person will receive in one year from the environment.**

Table 2: Estimated absorbed radiation dose from 0.5 mCi Lymphoseek in subjects with breast cancer and melanoma

Target Organ	Breast Cancer ^a mGy (rad)	Melanoma ^b mGy (rad)
brain	0.003 (0.0003)	0.0927 (0.0093)
breast (injection site)	1.659 (0.1659)	0.7903 (0.079)
gall bladder wall	0.0349 (0.0035)	0.0712 (0.0071)
lower large intestine wall	0.0123 (0.0012)	0.057 (0.0057)
small intestine	0.0101 (0.001)	0.0594 (0.0059)
stomach	0.0184 (0.0018)	0.0562 (0.0056)
upper large intestine wall	0.0125 (0.0012)	0.0582 (0.0058)
kidney	0.1863 (0.0186)	0.278 (0.0278)
liver	0.0324 (0.0032)	0.0929 (0.0093)
lungs	0.0374 (0.0037)	0.0599 (0.006)
muscle	0.0092 (0.0009)	0.0451 (0.0045)
ovaries	0.187 (0.0187)	0.2991 (0.0299)
red marrow	0.0127 (0.0013)	0.0507 (0.0051)
bone	0.0177 (0.0018)	0.0878 (0.0088)
spleen	0.0285 (0.0029)	0.0598 (0.006)
testes	0.0501 (0.005)	0.1043 (0.0104)
thymus	0.1168 (0.0117)	0.0577 (0.0058)
thyroid	0.088 (0.0088)	0.0464 (0.0046)
urinary bladder	0.0586 (0.0059)	0.1401 (0.014)
total body	0.0195 (0.0019)	0.0547 (0.0055)
Effective Dose Equivalent males females	microSv 296 330.2	microSv 202.4 251.1

^a Calculated from data of 18 patients with breast cancer who received four peritumoral injections of 4 mcg, 20 mcg, and 100 mcg doses of Lymphoseek.

^b Calculated from data of 18 patients with melanoma who received four intradermal injections of 20 mcg, 100 mcg, and 200 mcg doses of Lymphoseek. Due to the differences in injection sites among patients with melanoma, the injection site was assumed to be the breast for the purposes of this calculation, as it represents the nearest anatomical construct for the skin from the anatomical sites appropriately included in the estimates.

4.4 Definition of Dose-Limiting Toxicity (DLT)

AEs will be graded according to the CTCAE v5.0 (<http://evs.nci.nih.gov/ftp1/CTAE/about.html>).

Dose-limiting toxicity (DLT) will be defined as any Grade 2 or greater toxicity that is ALL of the following:

- Determined by the investigator to be possible, probably or definitely-related to panitumumab-IRDye800 or Lymphoseek
- Considered by the Investigator to be clinically significant for subjects who received panitumumab-IRDye800 or Lymphoseek. For this study, clinically significant is defined based on NCI definition – a result that is large enough to affect a subject's disease state in a manner that is noticeable to the subject and/or caregiver or requires intervention
- Occurred within 15 days of receiving treatment with panitumumab-IRDye800 or Lymphoseek

The Stanford Data Safety Monitoring Committee (DSMC) will be notified of all DLTs. The DSMC will evaluate safety data from all subjects through Day of discharge. If 3 or more subjects experience a DLT, then study enrollment will be halted pending DSMC review.

4.5 Surgical Imaging

Lymphadenectomy specimen assessment. Please see Section 2.4 for more detail. The neck will be imaged using near-infrared fluorescence and white light optical imaging systems and gamma tracing will be performed (Cohort 1 only). Imaging and tracing will be performed prior to lymphadenectomy, and after lymphadenectomy. Subsequently, the lymphadenectomy specimens will be imaged on a 'back table' prior to sending the specimens to pathology. The number and location of the fluorescent, and/or radioactive LNs will be documented.

The imaging information obtained will not be used for diagnosis or any other medical decision-making. Added surgical time for these images is expected to be minimal since these the images can be recorded for later review as still and video images. Once the specimens have been delivered to pathology, additional imaging will be performed as described above in Section 2.4.

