2.4 Study Design

- The primary purpose for the protocol is **Image Guidance**. The primary objective of the study is to determine if near-infrared fluorescence imaging of panitumumab-IRDye800 can identify metastatic disease in regional neck LNs of subjects with HNSCC.
- There are **2 cohorts**.
- The study is **open-label**. No masking is used.
- The study is **non-randomized**.
- The primary outcome is **number and location of LNs that are near-infrared fluorescent and that contain tumor as defined by (histo-)pathology**.

The study is an open-label study to determine if near-infrared fluorescence imaging of panitumumab-IRDye800 can identify metastatic disease in regional neck LNs of subjects with HNSCC. Panitumumab-IRDye800-based findings will be compared to LN biopsy and neck dissection. A schematic overview of the clinical trial is given in Figure 1.

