3. Hereafter, as per standard of care, the surgeon will perform SNB using the gamma probe. For this, the surgeon will evaluate the neck with the gamma probe for the presence of radioactive nodes. Upon localizing of radioactive nodes, the count rate of the node will be determined. Then, just prior to the resection of the radioactive node, *in situ* fluorescence imaging will be performed to evaluate the fluorescence-based visibility of the node. For each radioactive node, the respective *in situ* location will be documented (level Ia, Ib, IIa, IIb, III, IV or V) as well as the radioactive status (count rate) and fluorescence status (yes/no). Hereafter the node will be harvested by the surgeon. This process will be repeated until no radioactive nodes are detected anymore *in situ*.

Step 2) Wound bed imaging:

As per standard of care SNB, upon completion of SNB, the neck will be screened once more with the gamma probe as such to determine the presence of any remaining radioactivity (ie, a radioactive signal detected > 10% of the background that correlates with any substrate (node). Areas in the wound bed determined radioactive-positive will be surgically re-evaluated, and, upon checking the fluorescence-status, removed, if deemed necessary by the surgeon. If any nodes are found, gamma tracing will be performed to determine the radioactive status.

Step 3) Pathological imaging:

The fluorescence and/or radioactive status of all excised nodes will be confirmed *ex vivo* on the back table using both a closed-field imaging device and an open-field device as well as the gamma probe, respectively. Hereafter all excised nodal specimens will be sent for (histo-)pathology. After the tissue has been processed and evaluated by the pathologist, imaging findings will be compared to gold-standard histological-assessment performed by the pathologist (including a hematoxylin and eosin (H&E) staining) to determine the correlation between fluorescence, radioactivity and the presence/absence of tumor tissue in the LN(s). Also findings will be compared to preoperative lymphoscintigraphy and SPECT/CT imaging (ie, correlation between preoperative imaging findings and intraoperative imaging findings).

Neck dissection only (T1-4, cN+)

After the neck has been opened by the surgeon, it will be inspected by the surgeon for the presence of suspicious nodes. Real-time fluorescence imaging of the LNs in the neck will then be performed at 4 time points:

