Step 1) *In situ* imaging: After having opened the skin and exposure of the neck LNs, *in situ* fluorescence imaging will be performed to evaluate the fluorescence-based visibility of the LNs. For each fluorescent LN, the respective location will be documented (level Ia, Ib, IIa, IIb, III, IV or V) after which it will be harvested by the surgeon. This process will be repeated until no fluorescent LNs are seen *in situ*. Hereafter, the standard of care completion neck dissection will be performed.

Step 2) *Ex vivo* imaging: The neck dissection specimen will be evaluated for the presence of fluorescent LNs using both a closed-field imaging device and an open-field device. All additional fluorescent LNs will be identified, documented and collected separately; we acknowledge that the penetration depth of the fluorescence signal is limited and therefore deeper located LNs might not be detectable *in situ* (under step 1), but after having taken out the specimen and having “flipped” the specimen this might be possible.

Step 3) Wound bed imaging: This will be conducted for any remaining fluorescence (ie, any remaining fluorescent LNs). Areas in the wound bed determined fluorescence-positive will be surgically re-evaluated, and, if deemed necessary by the surgeon, removed.

Step 4) Pathological imaging: All excised nodal specimens will be imaged once more in the closed-field device to confirm that all fluorescent LNs have been removed from the neck dissection specimen. If not, the number and location of remainder fluorescent LNs will be documented after which they will be harvested; we will use the image taken under step 2 for reference as such to make sure that we did not create any confounding factor due to tissue

preparation to harvest nodes at step 2. Hereafter all excised nodal specimens will be sent for (histo-)pathology. After the tissue has been processed and evaluated by the pathologist, fluorescence imaging-based findings will be compared to gold-standard histological-assessment performed by the pathologist (including a hematoxylin and eosin (H&E) staining) to determine the correlation between fluorescence and the presence/absence of tumor tissue in the LN(s).

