12. STATISTICAL CONSIDERATIONS

12.1 Statistical Design

12.1.1. Primary Objective and Endpoint

The **primary objective** of the study is to determine if near-infrared fluorescence imaging of panitumumab-IRDye800 can identify metastatic disease in regional neck LNs of subjects with HNSCC.

The **primary endpoint** is: The number and location of panitumumab-IRDye800 positive LNs that are also tumor-positive at (histo-)pathology.

To **answer the primary objective**, we will calculate the sensitivity and specificity of the intraoperative findings on whether the LN is fluorescent (ie, presence of panitumumab-IRDye800) to the histopathological (gold standard) status of the LNs.

We will use the matched pair Durkalski's test (80), accounting for the cluster-correlation within subject, for all sensitivity and specificity comparisons (primary and secondary) using the clust.bin.pair package (81) in the R statistical software (84). Significance for both primary and secondary analyses will be assessed at the 0.05 level and to assess uncertainty, 95% confidence intervals will be provided for all estimates.

Descriptive statistics for continuous characteristics (eg, size of the tumor compartment) will include mean, standard deviation, median, interquartile range, minimum, and maximum values. Frequencies and percentages will be used to summarize categorical data. Graphical tools such as heat maps, histograms, and boxplots will be used to assess distributional properties of continuous variables.

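### In the neck dissection cohort, Section 4.5 bars any decision based on the imaging while Section 2.4.3.3 removes tissue because it fluoresces; tissue taken only for that reason would bias node-level accuracy, probably modestly

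*Combined protocol and SAP*

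**What the plan says.** Section 4.5 describes imaging of the neck before and after lymphadenectomy and of the specimens on the back table. It then says, with no exception, that "The imaging information obtained will not be used for diagnosis or any other medical decision-making". It refers the reader to Section 2.4 for detail.

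Section 2.4.3.3 sets out the steps for Cohort 2. At Step 1 the level of each fluorescent node is recorded, "after which it will be harvested by the surgeon. This process will be repeated until no fluorescent LNs are seen" in situ. The next sentence reads: "Hereafter, the standard of care completion neck dissection will be performed". Step 2 images the specimen and collects further fluorescent nodes from it. Step 3 returns to the patient: "Areas in the wound bed determined fluorescence-positive will be surgically re-evaluated, and, if deemed necessary by the surgeon, removed".

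For Cohort 1 (sentinel node biopsy) the same section makes the gamma probe the trigger: "Areas in the wound bed determined radioactive-positive will be surgically re-evaluated, and, upon checking the fluorescence-status, removed, if deemed necessary by the surgeon".

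The primary analysis in Section 12.1.1 is at node level: "we will calculate the sensitivity and specificity of the intraoperative findings on whether the LN is fluorescent", judged against histopathology. It gives no rule for nodes that were obtained only because they fluoresced. Section 2.4 says of the design that "No masking is used".

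**The concern.** There are two linked problems.

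The first is textual. Taking out a node, or going back into a wound bed, because it fluoresces is an intraoperative decision based on the image. Section 4.5 rules that out and Section 2.4.3.3 instructs it.

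The second is statistical. Sensitivity and specificity are unbiased only if the decision to send tissue to histology does not depend on the test under study. Once the planned dissection is complete, fluorescent tissue in the wound bed may be removed and examined, while non-fluorescent tissue beside it stays in the patient. If nodes from such tissue are scored as fluorescent and pooled with the rest, they can add true positives and false positives. The matching false negatives and true negatives are never seen. At stake is the primary accuracy estimate of the trial.

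**Working it through.** **Which tissue is affected.** Taking the steps in order:

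- Cohort 2, Step 1, inside the planned field: the completion dissection follows, so these nodes reach histology whether or not they fluoresce. Only the order of removal changes, and sensitivity and specificity do not.
- Cohort 2, Step 1, outside the planned field: removed only because of fluorescence. Affected.
- Cohort 2, Step 2: nodes are picked from a specimen already removed. Not affected.
- Cohort 2, Step 3: removed after the dissection, prompted by fluorescence. Affected.
- Cohort 1: harvest and wound-bed removal are prompted by radioactivity; fluorescence is recorded or checked first. Not affected in the same way.

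**Inputs (Section 12.1.3).** 600 nodes in 20 subjects; 5 to 10% tumor-positive, that is 30 to 60; 7.5% prevalence for the power calculation, that is 600 × 0.075 = 45 positive and 555 negative nodes; lower sensitivity 0.75; lower specificity 0.8. Section 2.1 reports 97.2% sensitivity for the earlier agent, used here as an upper value.

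**The plan's own figure.** With 600/20 = 30 nodes per subject and an intra-class correlation of 0.005, the effective sample size is 600/(1 + 29 × 0.005) = 600/1.145 = 524, as stated. That gives 524 × 0.075 = 39.3 effective positive nodes. Effective size governs precision, not a point estimate, so the bias check uses actual node counts.

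**Sensitivity.** Let D be the positive nodes in the planned dissection, S the sensitivity there, and k the metastatic nodes added only because they fluoresced and scored as test-positive. The pooled estimate is (S × D + k)/(D + k). The documents do not give k; it is an assumption. For D = 45 and S = 0.75, S × D = 33.75, and k = 3 gives 36.75/48 = 0.766. For S = 0.75:

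| D | k = 0 | k = 1 | k = 3 | k = 5 | k = 10 |
|---|---|---|---|---|---|
| 30 | 75.0% | 75.8% | 77.3% | 78.6% | 81.25% |
| 45 | 75.0% | 75.5% | 76.6% | 77.5% | 79.5% |
| 60 | 75.0% | 75.4% | 76.2% | 76.9% | 78.6% |

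At S = 0.972 and D = 45 the shift is 0.06, 0.18, 0.28 and 0.51 points for k = 1, 3, 5 and 10. Over D = 30 to 60, S = 0.75 to 0.972 and k = 1 to 10, it runs from 0.05 to 6.25 points.

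**Specificity.** With j benign fluorescent nodes added to 555 negatives, the estimate is 0.8 × 555/(555 + j) = 444/(555 + j). This is 79.3% at j = 5 and 78.6% at j = 10; j is also an assumption.

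**The case against.** Several counter-arguments carry weight.

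- *Most fluorescence-led harvesting does no harm.* A reader might infer from Step 1 that every node taken because it fluoresced inflates sensitivity. The completion dissection that follows rules this out for in-field nodes. This objection stands.
- *Only one cohort is concerned.* A reader might extend the point to the whole trial. Table 1 places 10 of 20 subjects in Cohort 1, where radioactivity is the trigger. This stands.
- *The direction is not certain.* It is tempting to say that a fluorescence-triggered node can never be a false negative. Section 12.1.1 does not say which imaging step supplies the index reading. If it is Step 1, a metastatic node first seen at Step 3 is a Step 1 miss. With D = 45 and k = 3 the estimate would then be 33.75/48 = 70.3%, a fall. Step 3 also removes areas, which may contain non-fluorescent nodes. The upward bias is therefore conditional on scoring these nodes as test-positive.
- *The shift is small against sampling error.* At 75% on 39 effective positive nodes, the 95% half-width is about 1.96 × √(0.75 × 0.25/39) = 13.6 points. In addition, k = 10 would mean one metastatic node per Cohort 2 subject left after dissection and found only by fluorescence, which nothing in the documents supports. This stands as to size.
- *Step 3 leaves removal to the surgeon.* This tempers the conflict but does not remove it: the re-evaluation is still prompted by the image, and Step 1 states no such discretion.

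A reader might also infer that subjects or the IRB were misinformed. The documents do not support that: the consent pages are not part of the reviewed text, and under Section 11.1 the IRB reviews the protocol, which contains both sections.

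**Conclusion.** The conflict between Section 4.5 and the Cohort 2 steps of Section 2.4.3.3 is real and has to be reconciled. The verification bias is also real but narrow. It is confined to Step 3 wound-bed tissue and to fluorescent nodes outside the planned field, and it takes the stated direction only if these nodes are scored as test-positive. At 45 positive nodes and 75% sensitivity, the inflation is 0.5 points for one such metastatic node and 4.5 points for ten. It is nil for none and smaller if true sensitivity is higher. Because the number of such nodes is assumed, the documents support calling the bias probably modest, and no more than that.

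**What to change.** 1. Reconcile Section 4.5 with Section 2.4.3.3 for Cohort 2. Which surgical rule applies is for the sponsor to settle.
2. Add a CRF field, completed at surgery, for each specimen removed only because of fluorescence and outside the planned standard-of-care dissection. If this is not recorded at the time, such nodes may not be separable later.
3. State in Section 12.1.1 that primary sensitivity and specificity use all nodes within the planned dissection, expressly keeping in-field nodes first picked out at Steps 1 and 2. Without that wording, a rule excluding tissue taken because of fluorescence would drop the Step 1 true positives and keep the misses, which is a worse bias than the one being corrected.
4. Report flagged tissue separately as additional yield, with a sensitivity analysis that includes it and states which imaging step is taken as the index reading.

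The cost is a wording amendment, one CRF field, one analysis rule, and slightly fewer nodes in the primary analysis.
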